25. Consent Process	13
26. Documentation of Consent	16
27. Study Test Results/Incidental Findings	16
28. Sharing Study Progress or Results with Subjects	17
29. Inclusion of Vulnerable Populations	18
30. Community-Based Participatory Research	19
31. Research Involving American Indian/Native Populations	19
32. Transnational Research	19
33. Drugs or Devices	20
Checklist Section	21
34. Export Control	22

PROTOCOL TITLE: Double-blind, placebo-controlled, randomized study of the safety and tolerability of isoxsuprine HCL combined with high dose steroid treatment of multiple sclerosis (MS) relapse

1. Objectives

Primary Objective

The primary objective of this study is to:

- Assess the safety and tolerability of Isoxuprine (ISX) in combination with high dose corticosteroids in subjects experiencing acute relapses due to multiple sclerosis.

The safety analysis population will include all randomized subjects who receive at least one dose of study drug. Safety endpoints will be summarized by treatment group (ISX or placebo) from the time of the first dose and include all available safety data. No formal statistical testing will be done. All adverse event data will be listed and will be summarized by treatment group. Quantitative safety variables (vital signs) will be summarized at each visit by treatment group and changes from baseline will be summarized by treatment group at selected visits.

Secondary Objective

The secondary objective of this study is to:

- Evaluate the potential efficacy of Isoxuprine as add-on treatment for improving neurological deficits in walking ability, visual acuity, and other associated symptoms of MS, including fatigue and cognitive dysfunction in this MS population experiencing a relapse.

The efficacy analyses will include all randomized and dosed subjects who provide Week 12 efficacy data. The key secondary analysis will compare the changes in EDSS functional system scores most relevant to the relapse associated disability (e.g. pyramidal, visual, cerebellar). Also walking speed and z-score from the Multiple Sclerosis Functional composite score (MSFC) from Baseline to Week 12 in the ISX group compared to the placebo group.

2. Background

Overview

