Those currently on MS disease modifying therapy will have received a stable regimen of the medications for at least 30 days prior to screening and will continue the same doses and regimens for the duration of their study participation.

Consented subjects will be assessed for relapse criteria and those who meet study eligibility criteria and agree to be treated with a standard 3 to 5 day pulse of high dose corticosteroids, will be randomized with equal probability to 1 of 2 treatment groups: placebo capsule or active Isoxsuprine (ISX).

The Screening Visit will take place within 7 days of relapse onset and within 48 hours of initiating high dose steroids. Subjects may start corticosteroids anytime during this 7 day window. During the screening period, subjects will be assessed with the Expanded Disability Status Scale (EDSS), Multiple Sclerosis Functional Composite (MSFC), and cognitive testing prior to treatment with ISX or placebo (1:1 ratio).

Safety Assessments during screening will include a physical exam, electrocardiogram, vital signs, weight and a urine pregnancy test for females of child bearing potential. At 7 (\pm 1) days following the completion of the 5-day ISX dosing, subjects will be re-assessed with the EDSS.

Subjects will be evaluated for treatment response using the EDSS and other standard measures described below at visits 1, 4 and 12 weeks.

Study drug will be administered as one (1) 10 mg capsule, 3 times daily for 5 days in conjunction with concomitant dosing with high dose corticosteroids. This can be any accepted regimen, including daily iv methylprednisolone 1000 mg/day or 600mg oral

PROTOCOL TITLE: Double-blind, placebo-controlled, randomized study of the safety and tolerability of isoxsuprine HCL combined with high dose steroid treatment of multiple sclerosis (MS) relapse

prednisone two times a day at approximately 8AM and noon, with food, as typically provided by UNM MS Specialty Clinic

4. Inclusion and Exclusion Criteria

Inclusion Criteria

Subjects must meet all the following criteria for inclusion in the study at the Screening Visit:

1. Subjects must be adequately informed and understand the nature and risks of the study and must be able to provide a signature and date on the ICF;
2. Male or female subjects between 18 and 50 years of age, inclusive;
3. Confirmed diagnosis of Multiple Sclerosis or Clinically Isolated Syndrome (CIS) suggestive of MS, according to the 2010 Revised McDonald criteria.

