- Treat with oral prednisone (600 mg BID) if not already receiving corticosteroid pulse, which can be via Iv or Po route.
- Adverse events and concomitant medications.

Randomization Visit (Visit 1) Procedures/Assessments

- Initiate treatment with Isoxsuprine HCL (oral) Capsule 10mg or placebo.
- 1 hour monitoring post dose.
- Vital signs.
- Electrocardiogram (ECG) post dose.
- Adverse events.

1 Week Post Treatment Safety Follow-Up Visit (Visit 2) Procedures/Assessments

The following procedures will be performed at this visit:

- Physical examination.
- EDSS.

PROTOCOL TITLE: Double-blind, placebo-controlled, randomized study of the safety and tolerability of isoxsuprine HCL combined with high dose steroid treatment of multiple sclerosis (MS) relapse

- Multiple Sclerosis Functional Composite (MSFC).
- Vital signs.
- Adverse events and concomitant medications.

4 Week Post Treatment Safety Follow-Up Visit (Visit 3) Procedures/Assessments

The following procedures will be performed at this visit:

- Physical examination.
- EDSS.
- Multiple Sclerosis Functional Composite (MSFC).
- Cognitive Battery (Symbol Digit Modality).
- Vital signs.
- Adverse events and concomitant medications.

12 Week Post Treatment Safety Follow-Up Visit (Visit 4) Procedures/Assessments

The following procedures will be performed at this visit:

- Physical examination.
- EDSS.
- Multiple Sclerosis Functional Composite (MSFC).
- Cognitive Battery (Symbol Digit Modality).
- Vital signs.
- Adverse events and concomitant medications.

Adverse Events

Adverse events will be recorded from signing of the ICF and followed by the investigator until the AE is resolved or stabilized. Any and all safety measures (which includes standard of care activities) should be provided by the study site to the subject. Any study site follow-up should be documented.

Medical History

Medical history will be obtained at the Screening Visit. Medical history will include a review of the following systems: general medical and surgical history. Historical and current medical conditions including date of last menstrual period for female subjects will be recorded.

Current Medical Conditions

At each visit after screening, subjects will be asked about any changes in medical conditions, specifically new medical conditions and worsening of existing medical conditions. Any changes since the Screening Visit will be recorded as AEs, as appropriate.

Physical Examination

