This study proposes to use isoxsuprine HCl (ISX) in standard 10 mg tablets in subjects experiencing an acute relapse of multiple sclerosis. The rationale comes from strong preclinical observations that ISX had significant and novel neuroprotective action in ischemic stroke using a cell-based high-throughput screening (PLOS ONE, 1 May 2014, Volume 9 (5) e9676.). Isoxsuprine was identified as a top neuroprotectant among 1,200 compounds in the Prestwick Chemical Library, which contains diverse, mostly FDA-approved and off-patent compounds, and its neuroprotective function was confirmed in transient ischemic injury in animals. ISX has been used in the past for suppressing premature labor and for vascular dementia, since the drug is a beta-adrenergic agonist and vasodilator. These older indications are not used very often now but a typical dose was 10mg by mouth 3 to 4 times per day. In this tolerability and safety study we will use 10mg tid as the dose, given for 5 consecutive days. The primary goal is to assess safety and tolerability in MS patients in a relapse, who are also receiving a short course of high dose steroids to shorten relapse recovery. These subjects are otherwise healthy and will not have significant other health issues. We do not anticipate adverse reactions to concomitant use of ISX and steroids. While ISX tends to lower blood pressure modestly, steroids tend to increase, essentially in offsetting directions. Subjects will be randomized to ISX 10mg tid x 5 days or matching placebo. They will initiate the ISX within 48 hours of starting steroids.

PROTOCOL TITLE: Double-blind, placebo-controlled, randomized study of the safety and tolerability of isoxsuprine HCL combined with high dose steroid treatment of multiple sclerosis (MS) relapse

Checklist Section

This section contains checklists to provide information on a variety of topics that require special determinations by the IRB. Please complete all checklists relevant to your research.

I. Waivers or Alterations of Consent, Assent, and HIPAA Authorization

Partial Waiver of HIPAA Authorization for Screening/Recruitment

Complete the following additional questions/attestations if the records you will review to identify potential subjects and/or determine eligibility include Protected Health Information (PHI).

1. Will you be recording any PHI when conducting the records review to identify potential subjects and/or determine eligibility?

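### Adverse events are summarised by arm over about 12 weeks with no split by period, although study drug is taken for 5 days; a by-period summary should be added

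*Protocol*

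**What the plan says.** Section 1 gives the primary objective as follows: "Assess the safety and tolerability of Isoxuprine (ISX) in combination with high dose corticosteroids in subjects experiencing acute relapses due to multiple sclerosis". That section also fixes how safety is summarised: "Safety endpoints will be summarized by treatment group (ISX or placebo) from the time of the first dose and include all available safety data". It adds "No formal statistical testing will be done".

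For AEs the only stated breakdown is by arm: "All adverse event data will be listed and will be summarized by treatment group". Vital signs are given a time structure: "Quantitative safety variables (vital signs) will be summarized at each visit by treatment group". The protocol defines no on-treatment window and no split of AEs by period.

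Exposure is short. Section 3: "Study drug will be administered as one (1) 10 mg capsule, 3 times daily for 5 days"; Section 26 (IND Waiver Justification): "In this tolerability and safety study we will use 10mg tid as the dose, given for 5 consecutive days". AE collection is long. Section 10: "Adverse events will be recorded from signing of the ICF and followed by the investigator until the AE is resolved or stabilized", with AEs recorded at visits out to Week 12.

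**The concern.** The stated summary window does not match the primary question. The reactions that Section 11 (Treatment Discontinuation) links to oral isoxsuprine, such as hypotension, tachycardia, nausea, dizziness and rash, would be expected mainly while the drug is being taken. Most of the window lies after dosing. In that time both arms continue to accrue events from MS, relapse recovery and ordinary illness, and an event in Week 9 counts the same as one on Day 2. Events that are equally likely in both arms pull an overall AE comparison towards no difference.

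The other planned safety data fill little of the gap. Under Section 26 the first dose is given in clinic with at least 1 hour of observation, and later doses are taken at home. The next scheduled visit is about a week after dosing ends (Section 3). Vital signs by visit therefore include no scheduled on-drug reading after the first dose. For the other 14 of the 15 doses (3 × 5 = 15), AE and symptom reports are nearly the only planned tolerability evidence. Section 15 says the pilot data may support starting a larger efficacy study, so the way these reports are summarised matters.

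**Working it through.** The target of 20 subjects (Section 5) comes with no AE rate, effect size or power, so there is no figure of the plan's own to reproduce.

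**Inputs from the protocol**
- Dosing: 5 days (Sections 3 and 26).
- Follow-up: up to 12 weeks = 84 days (Section 6). If the last visit is counted as 12 weeks after treatment, as its Section 10 label suggests, 84 + 5 = 89 days.
- Allocation: 20 subjects, 1:1, so 10 per arm (Section 5).
- Week 1 visit: 7 ± 1 days after dosing ends (Section 3).

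**Step 1: share of the window on drug**
- 5/84 = 6.0%, leaving 79 days off drug.
- 5/89 = 5.6%, leaving 84 days off drug.

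**Step 2: dilution of a subject-level AE proportion**

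Let p be the probability of at least one AE during dosing in an arm. Let q be the probability of at least one AE with onset after dosing, assumed equal in both arms and independent of events on drug. Over the whole window:

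P = 1 − (1 − p)(1 − q), so the difference between arms = (1 − q) × (p_ISX − p_placebo).

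The direction holds for any q above 0. For illustration only, assume p = 20% on placebo and 50% on ISX. With 10 per arm, SE = √(ΣP(1 − P)/10).

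| q (assumed) | Placebo | ISX | Difference | Ratio | Difference/SE |
|---|---|---|---|---|---|
| 0 (dosing period only) | 20% | 50% | 30 points | 2.50 | 1.48 |
| 20% | 36% | 60% | 24 points | 1.67 | 1.11 |
| 40% | 52% | 70% | 18 points | 1.35 | 0.84 |
| 60% | 68% | 80% | 12 points | 1.18 | 0.62 |
| 80% | 84% | 90% | 6 points | 1.07 | 0.40 |

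Starting from 10% v 40%, or 30% v 60%, gives the same differences, because only q enters the shrinkage factor.

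**Step 3: a single symptom that is rare off drug**

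If q for one symptom is 5% (assumed), a 30-point difference becomes 0.95 × 30 = 28.5 points. The loss is negligible.

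**Step 4: event counts instead of proportions**

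Take Poisson means of 0.2 v 0.5 per subject during dosing (assumed) and add an off-drug mean of 1 to each arm. The difference stays at 0.3. The ratio falls from 0.5/0.2 = 2.50 to 1.5/1.2 = 1.25. The SE rises from √(0.7/10) = 0.265 to √(2.7/10) = 0.520, so difference/SE falls from 1.13 to 0.58.

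**Step 5: would a window to the Week 1 visit be enough?**

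First dose to the Week 1 visit is about 5 + 7 = 12 days, of which 7/12 = 58% is off drug (6/11 = 55% to 8/13 = 62% with the ± 1 day). That window is itself mostly off drug, so the dosing days need their own column.

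**The case against.** The strongest reply is that the sentence in Section 1 is not wrong. Starting at first dose and discarding nothing is sound safety reporting. The text does not forbid a by-period table, and an analysis plan that is not shown may define one. The protocol names no any-AE proportion as its tolerability measure: Section 7 lists individual GI symptoms, AEs, vital signs and ECG parameters. All AEs are listed, and with about 10 subjects per arm the listing can be read event by event. First-dose monitoring, the discontinuation criteria in Section 11 and reporting to the safety board (Section 26) also bring acute problems to light. Nothing is tested, and no go/no-go threshold depends on an AE percentage.

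Most of this stands, and it limits the point. It does not remove it, because the protocol itself states the AE window and breakdown and gives vital signs a time structure that AEs lack. A listing is also not a planned comparison by arm, and a period chosen after the data are seen is weaker than one fixed beforehand.

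A reader might infer more: that the summary will make a poorly tolerated drug look like placebo, or that a 30-point difference will shrink to a few points. The document does not support that. Such figures need a high assumed off-drug rate and all kinds of AE collapsed into one yes/no measure. Nor are steroid effects during dosing a contaminant, since the objective concerns the combination.

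**Conclusion.** The point holds as a modest improvement to the stated method. The protocol summarises AEs by arm over a window of which about 6% is on drug, and it has no split by period. An overall AE comparison is diluted by (1 − q) under the assumptions of Step 2. Because the protocol gives no AE rates, the size cannot be determined. It ranges from negligible for a symptom rare off drug to substantial for an any-AE proportion with a high background rate.

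The harm is to a descriptive comparison, not to power or type I error. Even undiluted, a 30-point difference with 10 per arm is only about 1.5 standard errors, so a by-period table makes the evidence clearer to read but cannot make it conclusive. It would be wrong to infer that later events should be dropped or that the all-data summary is invalid.

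**What to change.** Keep the all-data summary and the listing. Add to the safety paragraph of Section 1 that AEs will also be summarised by arm and by period of onset:

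1. first dose to last dose;
2. after last dose to the Week 1 visit;
3. after the Week 1 visit to Week 12.

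State that acute tolerability will be read mainly from period 1, with period 2 shown beside it. If an analysis plan already contains such a table, align the protocol sentence with it.

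The cost is one sentence and one more table. It needs AE onset dates and each subject's date of last dose; the latter can be taken at Visit 2, where drug accountability is already checked. The downsides are small: cells will hold few events, and a delayed effect will appear in period 2 or 3, both of which are still reported.

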A complete physical examination will be performed at all four study visits. The complete physical examination includes evaluation of the head, eyes, ears, nose, throat, neck

PROTOCOL TITLE: Double-blind, placebo-controlled, randomized study of the safety and tolerability of isoxsuprine HCL combined with high dose steroid treatment of multiple sclerosis (MS) relapse

(including thyroid), cardiovascular system, lungs, abdomen, neurological system not obtained with EDSS, skin, extremities and other conditions of note.

The findings of the physical examinations will be recorded. Any change from the Screening Visit physical examination that is considered clinically significant by the investigator will be recorded as an AE.

Electrocardiogram

A 12 lead ECG will be taken at visits baseline and 1 week, (pre and post dose for visit 1).

Height and Weight

Height and Weight will be collected at screening only.

Vital Signs

Vital signs will be obtained after the subject has been seated for 5 minutes (minimum) and will include systolic and diastolic blood pressures, pulse rate, respiratory rate, and body temperature. Additionally, at the Screening/Randomization Visit, blood pressure will be measured at least 3 times, with 5 minutes between assessments after the subject has been seated for a minimum of 5 minutes prior to the initial blood pressure assessment. The date and time for all vital sign assessments will be recorded.

The investigator may perform additional unscheduled vital sign measurements to evaluate or manage a suspected AE. These unscheduled vital sign measurements should be obtained after the subject has been seated for at least 5 minutes, if possible. Unscheduled vital signs will be recorded.

Urine Pregnancy Tests

Urine pregnancy Tests will be completed at visit 1 on females of child bearing potential based on medical history obtained at screening visit.

Symbol Digit Modality Test

SDMT has demonstrated sensitivity in detecting not only the presence of cognition impairment, but also changes in cognitive functioning over time and in response to treatment. The SDMT is brief, easy to administer, and involves a simple substitution task that normal adults can easily perform. SDMT will be administered by a qualified examiner.

11. Withdrawal of Subjects

Subject Withdrawal

Subjects who discontinue, the reason for discontinuation will be recorded. A subject may be discontinued from the study for the following medical or administrative reasons:

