Not applicable. We will not be collecting any specimens or banking any data for this study protocol.

PROTOCOL TITLE: Double-blind, placebo-controlled, randomized study of the safety and tolerability of isoxsuprine HCL combined with high dose steroid treatment of multiple sclerosis (MS) relapse

14. Risks to Subjects

Along with its needed effects, isoxsuprine may cause some unwanted effects. Although not all of these side effects may occur, if they do occur they may need medical attention. Check with your doctor as soon as possible if any of the following side effects occur while taking isoxsuprine:

Rare

- Chest pain
- dizziness or faintness (more common for injection)
- fast heartbeat (more common for injection)
- shortness of breath
- skin rash

Some side effects of isoxsuprine may occur that usually do not need medical attention. These side effects may go away during treatment as your body adjusts to the medicine. Also, your health care professional may be able to tell you about ways to prevent or reduce some of these side effects. Check with your health care professional if any of the following side effects continue or are bothersome or if you have any questions about them:

Less Common

- Nausea or vomiting (more common for injection)

Risks to patient confidentiality will be mitigated by good clinical practice procedures as outlined in the protocol. Part of this study is a standard of care treatment for MS relapse and only the addition of isoxsuprine or placebo is the subject of the research. All patients will be screened and excluded for pregnancy

Careful examination and history will be taken to ascertain key inclusion and exclusion criteria in order to minimize the probability and magnitude of risks.

15. Potential Benefits to Subjects

This is not an efficacy study. The goal here is to study a reasonable number of MS patients in acute relapse who are receiving standard high dose steroid therapy. We will randomize 20 subjects to receive ISX or PBO and assess for any tolerability or safety issues as described in the protocol. Based on this pilot data, it may be reasonable to initiate a larger efficacy study. It is possible that ISX will in fact have neuroprotective properties in MS patients. In that scenario, patients could attain some benefit to their future disability. Again, this is not an endpoint and the study is not powered to detect a clinical benefit.

16. Recruitment Methods

Recruitment

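### The efficacy analyses are restricted to dosed subjects with Week 12 data, a post-randomisation condition that can bias the ISX-placebo comparison and sets aside Week 1 and Week 4 data already collected

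*Protocol*

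**What the plan says.** Section 1 (Secondary Objective) defines the efficacy set: "The efficacy analyses will include all randomized and dosed subjects who provide Week 12 efficacy data". The wording covers the efficacy analyses in general and makes no exception. The comparison that follows is of changes "from Baseline to Week 12 in the ISX group compared to the placebo group".

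The safety set in the same section carries no completion condition: "The safety analysis population will include all randomized subjects who receive at least one dose of study drug". Safety is summarised "from the time of the first dose and include all available safety data".

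Efficacy is measured before Week 12. Section 3 says: "Subjects will be evaluated for treatment response using the EDSS and other standard measures described below at visits 1, 4 and 12 weeks". Section 10 schedules EDSS and MSFC at the Week 1, 4 and 12 visits, and the SDMT at Weeks 4 and 12 (for Week 4, see "4 Week Post Treatment Safety Follow-Up Visit (Visit 3) Procedures/Assessments").

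Section 11 foresees departures: "A subject may be discontinued from the study for the following medical or administrative reasons". Its list comprises the subject's own withdrawal, an adverse event, death, loss to follow-up and the investigator's discretion.

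Section 15 plays down efficacy: "Again, this is not an endpoint and the study is not powered to detect a clinical benefit".

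**The concern.** Randomisation makes the arms comparable at the start. It does not make the survivors of a later selection comparable. Providing Week 12 data is such a selection, and several of the exit reasons in section 11 can depend on how well the subject tolerates treatment or recovers from the relapse. If poor responders leave one arm more than the other, that arm looks better than it is.

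The rule also has a cost in information. A subject assessed at Weeks 1 and 4 who then drops out contributes to no efficacy analysis, although both assessments say something about the likely Week 12 result. With 20 subjects, each loss is 1/10 = 10% of an arm.

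What is at stake is the secondary efficacy estimate. Section 3 calls the trial a proof of concept, and section 15 says the pilot data may support a larger efficacy study, so the estimate may be used even though it is not powered.

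**Working it through.** **No figure to reproduce.** The protocol states no efficacy effect size, SD, power or dropout rate. The figures below illustrate the mechanism and are not predictions.

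**Inputs from the protocol.** 20 subjects (section 5), randomised 1:1 (section 26), hence 10 per arm. Post-baseline efficacy visits at Weeks 1, 4 and 12 (sections 3 and 10).

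**Assumptions.** No true effect. Week 12 change normal with SD 1, lower being better. Correlation rho between Week 4 and Week 12 of 0.5, 0.7 or 0.9. 1, 2 or 3 of 10 lost per arm. Only Weeks 4 and 12 are modelled.

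**Step 1: selection shift.** The three largest of 10 standard normal values have expectations of about 1.539, 1.001 and 0.656. The full sample has expectation 0, so removing the worst k shifts the mean of those who stay by their sum divided by (10 − k):
- k = 1: 1.539/9 = 0.171
- k = 2: (1.539 + 1.001)/8 = 0.318
- k = 3: (1.539 + 1.001 + 0.656)/7 = 0.457

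**Step 2: absolute bias of the completer difference (SD units).**
- (a) Random loss, or the same mechanism at the same rate in both arms: 0.
- (b) One arm's loss follows a logistic model on Week 4 (odds ratio 3 per SD worse); the other arm's is random. Numerical integration gives a Week 4 shift among stayers of 0.098, 0.186 or 0.270 at 10, 20 or 30% loss. The bias is rho times this, from 0.5 × 0.098 = 0.049 to 0.9 × 0.270 = 0.243.
- (c) The worst Week 4 responders are lost in one arm, random loss in the other (extreme): rho times the step 1 values.
- (d) The worst Week 12 outcomes are lost in one arm, random loss in the other (most extreme): the step 1 values themselves.

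| 1 / 2 / 3 lost per arm | rho 0.5 | rho 0.7 | rho 0.9 |
|---|---|---|---|
| (c) completers | 0.09 / 0.16 / 0.23 | 0.12 / 0.22 / 0.32 | 0.15 / 0.29 / 0.41 |
| (d) completers | 0.17 / 0.32 / 0.46 | 0.17 / 0.32 / 0.46 | 0.17 / 0.32 / 0.46 |
| (c) Week 4 data used | about 0 | about 0 | about 0 |
| (d) Week 4 data used | 0.13 / 0.25 / 0.36 | 0.09 / 0.18 / 0.26 | 0.03 / 0.07 / 0.11 |

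The lower two rows come from simulation (40,000 replicates per cell). Each arm's Week 12 mean is adjusted to the Week 4 mean of all its subjects, using a slope common to both arms. Simulation of the completer rows agrees with the formulas to within Monte Carlo error.

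**Step 3: noise.** The standard error of the completer difference is √(2/m) with m per arm: √(2/9) = 0.47, √(2/8) = 0.50, √(2/7) = 0.53. The bias is below this in every case.

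**Step 4: precision.** With random loss of 2 per arm, using Week 4 data lowers the standard error from 0.50 to 0.49, 0.47 or 0.46 at rho 0.5, 0.7 or 0.9.

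**The case against.** The best case for leaving the rule alone is that little depends on it. Efficacy is secondary, the protocol disclaims power, no decision threshold hangs on the contrast, and the bias is smaller than the standard error even in the extreme cases. Bias also needs loss that is both outcome-related and different between arms, and nothing in the protocol points to that. Dosing is blinded and lasts 5 days, subjects must be willing to attend all visits, and stopping study drug is listed separately from leaving the study. This stands, and it limits the weight of the point. It does not justify the rule: a standard error describes random uncertainty and does not reveal a systematic shift.

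The remedy has limits too. Subjects who leave during the 5-day course have no post-baseline efficacy data to use. The near-zero bias in (c) follows by construction, because loss there depends only on Week 4. The gain in precision is small. The illustration uses a normal outcome, while EDSS functional system scores are ordinal. All of this stands.

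Two arguments do not succeed. The sentence might be meant only for the Week 12 comparison, which would leave the early visits free for other use; but the Week 12 comparison would still be completers-only, and that is where the bias arises. Nor can the point be left to a statistical analysis plan (not available here). The protocol itself fixes the set, and a plan that used all dosed subjects would contradict it. The details of the model can reasonably go in that plan.

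**Conclusion.** The concern holds. The protocol conditions its randomised efficacy comparison on an event after randomisation, and nothing elsewhere in it restores the excluded subjects. The harm comes from the Week 12 condition. The dosing condition matters little, because the first dose is blinded and supervised in clinic.

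The size depends on a dropout pattern that the protocol does not give. With 10 per arm and 10 to 30% loss, the bias runs from zero (random loss, or the same mechanism and rate in both arms), through 0.05 to 0.24 SD (moderate dependence on Week 4 in one arm), to 0.46 SD (the three worst Week 12 outcomes lost in one arm). It stays below the standard error throughout. The primary safety analysis is not affected. The rule should be fixed because doing so is cheap; it does not threaten the trial's main purpose.

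**What to change.** Replace the sentence in section 1 with text to this effect:

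> Efficacy will be analysed in every randomised subject who received study drug, in the arm assigned, using all available post-baseline assessments (Weeks 1, 4 and 12; Weeks 4 and 12 for the SDMT). The estimate is the ISX-placebo contrast at Week 12 from a repeated-measures analysis or, for EDSS functional system scores, a method suited to ordinal data. An analysis limited to subjects with Week 12 data is a sensitivity analysis. The number of dosed subjects without post-baseline efficacy data, and the reasons, will be reported by arm.

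The cost is wording and a little more analysis; no visits, data or patients are added. There are downsides:
- The analysis assumes data are missing at random given the earlier visits, so bias from loss that depends on unseen Week 12 outcomes is reduced but not removed (case d).
- It cannot recover subjects lost before the first post-baseline efficacy visit, 7 days after dosing ends.
- With 20 subjects the model must stay simple. At 30% loss and rho 0.5 in case (c), its standard error is about 0.01 SD higher than that of the completer analysis.
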